### 1.1 Background Information

To date, there have been 4 clinical studies completed using RBP-6000 ([Table 1](#)).

**Table 1** Summary of Completed RBP-6000 Clinical Studies

Study	Study Title	IMP (Dose)	Most Common AE(s) Possibly Related to Study Drug	Other Safety
RB-US-10-0011	A Single-Dose, Open-Label Study of Depot Buprenorphine (RBP-6000) in Opioid Dependent Individuals	RBP-6000 (20 mg)	Drug withdrawal syndrome Injection site pain Rebound hypertension Constipation Headache Injection site warmth Respiratory rate increased	No clinically significant trends in vital signs, ECGs, clinical laboratory tests, or physical examinations. No deaths or SAEs related to treatment and no subjects discontinued due to an AE.
RB-US-11-0020	A Multicenter, Open-Label, Single Ascending-Dose Study to Evaluate the Safety, Tolerability, and Pharmacokinetics of Depot Buprenorphine (RBP-6000) in Opioid-Dependent Subjects	RBP-6000 (50 mg, 100 mg, and 200 mg)	Drug withdrawal syndrome Constipation Diarrhea Nausea Injection site pain	No clinically significant trends in vital signs, ECGs, clinical laboratory tests, or physical examinations. No deaths or SAEs related to treatment and no subjects discontinued due to an AE.
RB-US-12-0005	An Open-Label, Multicenter, Multiple Dose Study of the Safety, Tolerability, Pharmacokinetics, Efficacy Markers, and Opioid Receptor Availability of Subcutaneous Injections of Depot Buprenorphine (RBP-6000) in Treatment Seeking Opioid Dependent Subjects	RBP-6000 (50 mg, 100 mg, 200 mg, and 300 mg)	Drug withdrawal syndrome Vomiting Constipation Musculoskeletal pain Anxiety Upper Respiratory Tract Infection Liver function test abnormal	No clinically significant trends in hematology, serum chemistry, urinalysis, vital signs, or ECGs. There were 9 SAEs during the study; 3 subjects withdrawn due to SAEs; 8 subjects withdrawn from the study due to a TEAE. None of the above events were considered related to study medication.
RB-US-13-0002	A Multiple-Dose Study of Blockade of Subjective Opioid Effects, Pharmacokinetics, and Safety of Subcutaneous Injections of Depot Buprenorphine (RBP-6000) in Subjects with Opioid Use Disorder	RBP-6000 (300 mg)	Drug withdrawal syndrome Headache Anxiety Constipation Liver function test abnormal Injection site reaction	No clinically significant trends in hematology, serum chemistry, urinalysis, vital signs, and ECGs. No deaths, no SAEs, and no withdrawals from the study due to a TEAE.

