12.1 ADVERSE EVENTS

12.1.1 Adverse Events

Imputation rules for AE (for determination of TEAE only) start date are in Section 20.7.

Treatment-emergent Adverse Events (TEAEs)

TEAEs are those that started following the first dose of RBP-6000 and before the Treatment End Date (the maximum of the date of the end-of-study/ Early Termination (EOS/ET) visit and the date of last injection + 28 days) in this study, or were present prior to the first dose of RBP-6000 regardless of causality and increased in severity within the treatment period (defined in section 20.1) AEs include those events that are ongoing at the time a subject rolls-over from the RB-US-13-0003.

Treatment-related Adverse Events

A summary of TEAEs will be presented for the Safety Analysis Set, including the number and percentage of subjects reporting at least one TEAE, the number and percentage of subjects with the following:

- Related TEAEs
- SAEs
- Related SAEs
- TEAEs with an outcome of death
- TEAEs
- Severe TEAEs
- TEAEs leading to RBP-6000 discontinuation

A breakdown of the number and percentage of subjects reporting each TEAE categorized by SOC and PT coded per the MedDRA dictionary version 19.0 will be presented in the Safety Analysis Set. Note that counting will be by subject not by event and subjects will be only counted once within each SOC or PT.

A further tabulation of events experienced by $\geq 5\%$ of subjects by SOC and PT will be presented for the Safety Analysis Set. If there are no TEAEs experienced $\geq 5\%$ of subjects by any PT, this table will be empty.

A summary of events reported, categorized by severity, will also be provided. Subjects with multiple events within a SOC or PT will be counted under the category of their most severe event within that SOC or PT. A further tabulation of severe AE/TEAEs will be presented by SOC and PT.

Additionally, treatment-related AEs/TEAEs will be summarized by maximum severity (mild, moderate, or severe). A breakdown of severe treatment-related AEs/TEAEs by SOC and PT will be provided.

All AEs (including non-TEAEs) recorded on the CRF will be listed.

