12.1.5 Potentially Pertaining to Drug Withdrawal Symptoms

A summary of TEAEs potentially pertaining to drug withdrawal during the Treatment Period, as defined in [Appendix 1](#), will be summarized by SOC and PT for the Safety Analysis Set.

Additionally, A summary table of Adverse Events potentially pertaining to drug withdrawal during the Safety Follow-up Period will be used to tabulate AEs related to drug withdrawal symptoms in the Safety Follow-Up period after EOS/ET visit, if any.

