Panic attack	Antisocial personality disorder
Panic disorder	Borderline personality disorder
Panic reaction	Histrionic personality disorder

Compulsions	Narcissistic personality disorder
Obsessive thoughts	Psychopathic personality
Obsessive-compulsive disorder	Paranoid personality disorder
Trichotillomania	Schizoid personality disorder
Body dysmorphic disorder	Schizotypal personality disorder
Obsessive rumination	Breath holding
Dermatillomania	Staring
Compulsive lip biting	Regressive behaviour
Nail picking	Abnormal behaviour
Compulsive shopping	Sexually inappropriate behaviour
Compulsive hoarding	Behaviour disorder due to a general medical condition
Compulsive handwashing	Scatolia
Paediatric autoimmune neuropsychiatric disorders associated with streptococcal infection	Neglect of personal appearance
Trichotemnomania	Trance
Compulsive cheek biting	Hypervigilance
Obsessive need for symmetry	Abulia
Obsessive-compulsive symptom	Psychiatric symptom
Anxiety disorder due to a general medical condition	Psychiatric decompensation
Generalised anxiety disorder	Decreased eye contact
Neurosis	Psychological trauma
Postpartum neurosis	Helplessness
Selective mutism	Personality change due to a general medical condition
Separation anxiety disorder	Mental disorder due to a general medical condition
Anxiety disorder	Neuropsychiatric syndrome
Catatonia	Psychological factor affecting medical condition
Restlessness	Mental status changes
Automatism	Dyslogia
Automatism epileptic	Mental disorder
Automatism, command	Emotional disorder of childhood
Bruxism	Neurotic disorder of childhood
Echolalia	Personality disorder of childhood
Echopraxia	Reactive attachment disorder of infancy or early childhood
Head banging	School refusal
Posturing	Disinhibited social engagement disorder of childhood
Stereotypy	Encopresis
Waxy flexibility	Enuresis

Tic	Alcohol abuse
Chronic tic disorder	Alcohol problem
Complex tic	Alcoholic hangover
Provisional tic disorder	Alcoholism
Secondary tic	Dependence
Attention deficit/hyperactivity disorder	Drug abuse
Atypical attention deficit syndrome	Drug dependence
Oppositional defiant disorder	Drug dependence, antepartum
Conduct disorder	Drug dependence, postpartum
Disruptive mood dysregulation disorder	Tobacco abuse
Change in sustained attention	Withdrawal syndrome
Distractibility	Alcohol withdrawal syndrome
Daydreaming	Nicotine dependence
Executive dysfunction	Tobacco withdrawal symptoms
Vascular cognitive impairment	Neonatal complications of substance abuse

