Post-injection delirium sedation syndrome	Cerebrovascular accident
Preictal state	Dizziness
Psychogenic pseudosyncope	Dizziness exertional
Mental status changes	Dizziness postural
Mental status changes postoperative	Procedural dizziness
Slow response to stimuli	Neurotoxicity
Unresponsive to stimuli	

CMQ LIST OF PREFERRED TERMS FOR RESPIRATORY DEPRESSION/RESPIRATORY FAILURE

Acute respiratory distress syndrome	Neonatal respiratory arrest
Acute respiratory failure	Neonatal respiratory depression
Apnoea	Neonatal respiratory distress syndrome
Apnoea neonatal	Neonatal respiratory failure
Infantile apnoea	Respiratory arrest
Apnoeic attack	Respiratory depression
Bradypnoea	Respiratory depth decreased

Breath sounds absent	Respiratory distress
Cardio-respiratory distress	Respiratory failure
Central-alveolar hypoventilation	Respiratory paralysis
Chronic respiratory failure	Respiratory rate decreased
Hypopnoea	Severe acute respiratory syndrome
Hypoventilation	Cardio-respiratory arrest
Hypoventilation neonatal	Cardio-respiratory arrest neonatal
Lung hypoinflation	Cardiopulmonary failure
Meconium aspiration syndrome	

CMQ LIST OF PREFERRED TERMS FOR ORTHOSTATIC HYPOTENSION

Orthostatic hypotension	Syncope
Vision blurred	Presyncope
Dizziness	Diastolic hypotension
Dizziness exertional	Hypotension
Dizziness postural	

CMQ LIST OF PREFERRED TERMS FOR WITHDRAWAL SYMPTOMS

Agitation	Malaise
Anxiety	Muscle spasms
Arthralgia	Muscle twitching
Bone pain	Myalgia
Chills	Mydriasis
Decreased appetite	Nausea
Depression	Piloerection
Diarrhoea	Pruritus
Dizziness	Psychomotor hyperactivity
Drug dependence	Pyrexia
Flushing	Respiratory rate increased
Heart rate increased	Restlessness
Hyperhidrosis	Rhinitis
Hypertension	Rhinorrhoea
Hypervigilance	Sneezing
Influenza like illness	Tachycardia

Insomnia	Tremor
Irritability	Vomiting
Lacrimal disorder	Yawning
Lacrimation increased	Drug withdrawal symptoms
Muscle strain	

CMQ LIST OF PREFERRED TERMS FOR ACUTE PANCREATITIS

Amylase abnormal	Oedematous pancreatitis
Amylase creatinine clearance ratio abnormal	Pancreatic abscess
Amylase increased	Pancreatic enzyme abnormality
Bilirubin conjugated abnormal	Pancreatic enzymes abnormal
Blood bilirubin increased	Pancreatic enzymes increased
Blood trypsin increased	Pancreatic haemorrhage
Cullen's sign	Pancreatic necrosis
Grey Turner's sign	Pancreatic phlegmon
Haemorrhagic necrotic pancreatitis	Pancreatic pseudocyst
Hereditary pancreatitis	Pancreatic pseudocyst drainage
Hyperamylasaemia	Pancreatitis

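### The SAP's withdrawal term list names withdrawal only once and omits two withdrawal-syndrome wordings used elsewhere in the documents, so events coded to them would miss the withdrawal topic table

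*SAP*

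**What the plan says.** SAP 12.1.5 plans two withdrawal summaries. The first is "A summary of TEAEs potentially pertaining to drug withdrawal during the Treatment Period, as defined in" Appendix 1, shown by SOC and PT (Table 14.3.1.12). The second covers events after treatment: a table that "will be used to tabulate AEs related to drug withdrawal symptoms in the Safety Follow-Up period after EOS/ET visit, if any" (Table 14.3.1.13). The second sentence cites no list.

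Appendix 1 contains one withdrawal list, headed "CMQ LIST OF PREFERRED TERMS FOR WITHDRAWAL SYMPTOMS". Almost all its entries are single signs, symptoms or related conditions, such as nausea, yawning and anxiety. The only entry that names withdrawal is "Drug withdrawal symptoms". SAP 12.1.1 says the TEAE tables use "SOC and PT coded per the MedDRA dictionary version 19.0". Nothing in the SAP adds unlisted terms to the withdrawal topic.

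Protocol 1.1, Table 1, gives "Drug withdrawal syndrome" as the first entry among the most common possibly related AEs for each of the four completed RBP-6000 studies. The Psychiatric History list in SAP Appendix 1 contains "Withdrawal syndrome".

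**The concern.** The list is the selection rule for the withdrawal topic. It admits non-specific terms such as muscle strain, rhinitis and pyrexia. As printed, it would leave out an event coded as a withdrawal syndrome unless that event happened to be coded to the single withdrawal wording in the list. Given protocol Table 1, a reader would look for a withdrawal-syndrome row first.

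The follow-up period is the more exposed of the two. Under SAP 12.1.1, an event that starts after the Treatment End Date is not a TEAE, so it falls outside the overall TEAE table. Table 14.3.1.13 is the only table in Appendix 3 whose title is about AEs in follow-up. A new follow-up event missed there is certain to be found only in the AE listings. Whether the serious, severe and related tabulations would include it is unclear, because the SAP text and the Appendix 3 table titles differ on whether they are limited to TEAEs.

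**Working it through.** No figure in the plan needs to be reproduced. The check is a reading of the terms side by side.

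**1. Count the withdrawal list.** As printed in SAP Appendix 1 it has 21 terms in the left column and 20 in the right: 21 + 20 = 41. Entries containing the word withdrawal: 1 of 41. Entries matching either omitted wording: 0 of 41. The list runs without a break to the next heading, with no sign of redaction or a lost row.

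**2. Locate each wording.**

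| Wording | Withdrawal list | Psychiatric History list | Protocol Table 1 |
|---|---|---|---|
| "Drug withdrawal symptoms" | yes | no | no |
| "Drug withdrawal syndrome" | no | no | 4 of 4 studies |
| "Withdrawal syndrome" | no | yes | not as an entry of its own |
| "Drug dependence" | yes | yes | no |

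The second wording is in none of the Appendix 1 lists.

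**3. Test whether placement in the psychiatric list explains the omission.** If a term could belong to only one topic, its place there would account for the gap. But 8 of the 41 withdrawal terms are in both lists: agitation, anxiety, irritability, drug dependence, hypervigilance, restlessness, depression and insomnia. Terms are therefore shared freely between topics, and placement alone is not the reason.

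**4. Follow an event through the tables.**
- Treatment period, coded "Drug withdrawal syndrome": in Table 14.3.1.2 (all TEAEs); not in Table 14.3.1.12.
- Treatment period, coded "Withdrawal syndrome": in Tables 14.3.1.2 and 14.3.1.20 (psychiatric topic); not in Table 14.3.1.12.
- New event in follow-up, either code: in the AE listing; not in Table 14.3.1.13 if that table uses the same list.

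**5. Effect on counts.** The row for an omitted term is absent whenever such an event occurs. A count of subjects with any withdrawal-topic event changes only for subjects who have an omitted term and none of the 41 listed terms. That number lies between zero and the number of subjects with an omitted term. The documents give no event rates, so it cannot be narrowed further.

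**The case against.** The strongest reply is that the consequence depends on a dictionary the documents do not contain. Whether any event is lost turns on which wordings are MedDRA 19.0 preferred terms, and the printed entry may simply be a slip for the correct term. This stands as a limit on the size of the effect. It does not remove the mismatch. Appendix 1 presents "Withdrawal syndrome" as a preferred term, so by the SAP's own account a term of that name exists and is not in the withdrawal list.

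Protocol Table 1 is also weak evidence of frequency. It gives no counts and no dictionary. Two of its four studies are single-dose by title, one of them at 20 mg. Subjects here have already completed RB-US-13-0003, with up to 12 injections in that study, or up to 6 if they came from RB-US-13-0001. This is fair: Table 1 supports the comparison of wording, not an expectation of how often withdrawal will be reported.

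The table is descriptive, and no hypothesis or decision rests on it. Treatment-period events stay in the overall TEAE table, and subjects with nausea, anxiety, insomnia or diarrhoea are counted anyway. Protocol 9.5.1.1 does not call for a withdrawal topic table and excludes AEs that began after EOS from the safety analysis, so no protocol commitment is broken. All of this stands and keeps the point minor.

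Finally, since Appendix 1 has only one withdrawal list and the two table titles share their wording, the natural reading is that both tables use it. That is probably right. It also means the gap would carry into the follow-up table.

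**Conclusion.** The concern holds, as a minor point. The mismatch of terms is certain on the printed text: 1 of 41 terms names withdrawal, and neither omitted wording is among the 41. The omission from Table 14.3.1.12 is conditional on events being coded to an omitted term. The omission from Table 14.3.1.13 is conditional also on that table using the same list. Only the topic grouping is affected in the treatment period. The number of subjects is unknown and may be zero. High confidence applies to the mismatch and the conditional omission, not to any count of subjects.

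**What to change.** Before the tables are run, check the withdrawal list against MedDRA 19.0 and against the study's coded AE terms. Replace or supplement "Drug withdrawal symptoms" with the preferred term or terms to which drug or opioid withdrawal events are coded: "Drug withdrawal syndrome", "Withdrawal syndrome" or both, whichever are valid. In SAP 12.1.5, cite the Appendix 1 withdrawal list for both Table 14.3.1.12 and Table 14.3.1.13. Making the change at that point avoids adding a term after a missed event has been noticed, which would look data-driven.

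The cost is one or two terms in an appendix and one citation, with no new data. The only downside is that the reported incidence of withdrawal-topic events may be slightly higher.

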23.2 APPENDIX 2: LIST OF CYP3A4 INHIBITOR MEDICATIONS

Generic/Brand Name	Category	Generic/Brand Name	Category
Alprazolam	weak	isoniazid	weak
Amiodarone	weak	istradefylline	weak
Amlodipine	weak	Itraconazole	strong
Amprenavir	moderate	ivacaftor	weak
Aprepitant	moderate	Ketoconazole	strong
Atazanavir	moderate	lapatinib	weak
Atorvastatin	weak	lomitapide	weak
Bicalutamide	weak	lopinavir	strong

boceprevir	strong	Mestranol	weak
Chloramphenicol	unclassified	Metronidazole	unclassified
chlorzoxazone	weak	Mibepradil	strong
cilostazol	weak	Miconazole	unclassified
Cimetidine	moderate	Mifepristone	unclassified
Ciprofloxacin	moderate	Nefazodone	strong
Clarithromycin	strong	Nelfinavir	strong
Clotrimazole	moderate	Nicardipine	unclassified
cobicistat	strong	nilotinib	weak
conivaptan	strong	Norfloxacin	unclassified
crizotinib	moderate	Norfluoxetine	unclassified
Cyclosporine	moderate	ombitasvir	strong
danoprevir	strong	paritaprevir	strong
darunavir	moderate	pazopanib	weak
dasabuvir	strong	posaconazole	strong
Delavirdine	strong	Progestogen	weak
Diethyldithiocarbamate	unclassified	Propofol	unclassified
Diltiazem	strong	Quinine	unclassified
dronedarone	moderate	Ranitidine	weak
elvitegravir	strong	ranolazine	weak
Erythromycin	moderate	Ritonavir	strong
estradiol	weak	Saquinavir	strong
ethinyl	weak	Sertraline	unclassified
Fluconazole	moderate	Starfruit	unclassified
Fluoxetine	weak	tacrolimus	weak
Fluvoxamine	moderate	Telaprevir	strong
fosamprenavir	moderate	Telithromycin	strong
fosaprepitant	weak	ticagrelor	weak
Gestodene	weak	tipranavir	strong
ginkgo	weak	tofisopam	moderate
goldenseal	weak	troleandomycin	strong
grapefruit	strong	Verapamil	moderate
idelalisib	strong	voriconazole	strong

23.3

APPENDIX 3: TABLES, FIGURES AND LISTINGS

Tables

14.1 Demographic Data Tables & Figures

Table 14.1.1.1 Subject Disposition – All Screened Subjects
Table 14.1.1.2 Enrollment by Site – All Screened Subjects
Table 14.1.1.3 Enrollment by Site - Safety Analysis Set
Table 14.1.1.4 Subject Analysis Sets - All Screened Subjects
Table 14.1.2.1 Demographic and Baseline Characteristics – Safety Analysis Set
Table 14.1.3.1 Medical History - Safety Analysis Set
Table 14.1.4.1 Substance Use – Safety Analysis Set
Table 14.1.5.1 Summary of Prior Medications – Safety Analysis Set
Table 14.1.5.2 Summary of Concomitant Medications during RBP-6000 Dosing – Safety Analysis Set
Table 14.1.5.3 Summary of Concomitant Medications post RBP-6000 Dosing– Safety Analysis Set
Table 14.1.5.4 Summary of Subjects Who have taken CNS Depressant Medications during RBP-6000 Dosing (using Concomitant medication data and Urine Drug Screening)– Safety Analysis Set
Table 14.1.5.5 Summary of CNS Depressant Medications Taken during RBP-6000 dosing – Safety Analysis Set
Table 14.1.5.6 Summary of CYP3A4 Inhibitor Medications by Category (Unclassified, Weak, Moderate or Strong inhibitors) during RBP-6000 dosing – Safety Analysis Set
Table 14.1.5.7 Summary of CYP3A4 Inhibitor Medications by Category (Unclassified, Weak, Moderate or Strong inhibitors) post RBP-6000 dosing – Safety Analysis Set
Table 14.1.6.1 Summary of RBP-6000 Exposure – Safety Analysis Set
Table 14.1.6.2 Cumulative Frequency Distribution of RBP-6000 Exposure – Safety Analysis Set
Table 14.1.6.3 Summary of RBP-6000 Injections – Safety Analysis Set
Table 14.1.6.4 Cumulative Frequency Distribution of RBP-6000 Injections – Safety Analysis Set
Table 14.1.6.5 Dose Level Over Time During the Treatment Period – Safety Analysis Set
Table 14.1.6.6 Dose Level Over Time During the Treatment Period for Subjects Who Received 100 mg at the First Injection – Safety Analysis Set
Table 14.1.6.7 Dose Level Over Time During the Treatment Period for Subjects Who Received 300 mg at the First Injection – Safety Analysis Set
Table 14.1.6.8 Dose Modification and its Reason Over Time During the Treatment Period – Safety Analysis Set
Figure 14.1.6.8 Stacked Bar Chart of Dose Modification Over Time During the Treatment Period – Safety Analysis Set
Table 14.1.6.9 Frequency Distribution of Total Number of Injections in the Treatment Period by Dose Level – Safety Analysis Set
Table 14.1.6.10 Frequency Distribution of Days Since Last Injection During the Treatment Period – Safety Analysis Set
Figure 14.1.6.10 Distribution of Actual Injection Days Over Time During the Treatment Period – Safety Analysis Set

14.2 Efficacy Data Tables

Table 14.2.1.1 Cumulative Distribution Function of the Percentage of Urine Samples Negative for Opioids in the treatment period – Safety Analysis Set
Table 14.2.1.2 Number and Percentage of Subjects with Urine Samples Negative for Opioids by Visit – Safety Analysis Set
Table 14.2.1.3 Urine Toxicology for Drug Usage for All Visits in the Treatment Period – Safety Analysis Set

14.3 Safety Data Tables & Figures

Table 14.3.1.1 Overall Summary of Treatment-Emergent Adverse Events – Safety Analysis Set
Table 14.3.1.2 Summary of Treatment-Emergent Adverse Events by MedDRA System Organ Class and Preferred Term During the Treatment Period – Safety Analysis Set
Table 14.3.1.3 Summary of Treatment-Emergent Adverse Events Experienced by >=5% of Subjects by MedDRA Preferred Term During Treatment Period– Safety Analysis Set

Table 14.3.14 Summary of Treatment-Emergent Adverse Events Leading to Discontinuation by MedDRA System Organ Class and Preferred Term During Treatment Period- Safety Analysis Set

Table 14.3.1.5 Summary of Deaths due to Adverse Event (AE) - Safety Analysis Set

Table 14.3.1.6 Summary of Serious Treatment-Emergent Adverse Events by MedDRA System Organ Class and Preferred Term During Treatment Period- Safety Analysis Set

Table 14.3.1.7 Summary of Serious Treatment-Emergent Adverse Events Related to Study Treatment by MedDRA System Organ Class and Preferred Term During Treatment Period- Safety Analysis Set

Table 14.3.1.8 Summary of Treatment-Emergent Adverse Events by Maximum Severity, MedDRA System Organ Class and Preferred Term During Treatment Period – Safety Analysis Set

Table 14.3.1.9 Summary of Treatment-Emergent Adverse Events Related to Study Treatment by Maximum Severity, MedDRA System Organ Class and Preferred Term During the Treatment Period- Safety Analysis Set

Table 14.3.1.10 Summary of Severe Treatment-Emergent Adverse Events Related to Study Treatment Leading to Discontinuation by MedDRA System Organ Class and Preferred Term During the Treatment Period- Safety Analysis Set

Table 14.3.1.11 Summary of Severe Treatment-Emergent Adverse Events by MedDRA System Organ Class and Preferred Term During the Treatment Period- Safety Analysis Set

Table 14.3.1.12 Summary of Treatment-Emergent Adverse Events Potentially Pertaining to Drug Withdrawal Symptoms by MedDRA System Organ Class and Preferred Term During the Treatment Period- Safety Analysis Set

Table 14.3.1.13 Summary of Treatment-emergent Adverse Events Potentially Pertaining to Drug Withdrawal Symptoms During the Safety Follow-up Period for Subjects Who Entered into the Safety Follow-up Period

Table 14.3.1.14 Summary of Treatment-Emergent Adverse Events Potentially Pertaining to Injection Site Reactions by MedDRA System Organ Class and Preferred Term During the Treatment Period- Safety Analysis Set

Table 14.3.1.15 Summary of Treatment-Emergent Adverse Events Potentially Pertaining to Acute Pancreatitis by MedDRA System Organ Class and Preferred Term during the Treatment Period - Safety Analysis Set

Table 14.3.1.16 Summary of Treatment-Emergent Adverse Events Potentially Pertaining to Hepatic Disorders by MedDRA System Organ Class and Preferred Term during the Treatment Period - Safety Analysis Set

Table 14.3.1.17 Summary of Treatment-Emergent Adverse Events Potentially Pertaining to Respiratory Depression and Failure by MedDRA System Organ Class and Preferred Term during the Treatment Period - Safety Analysis Set

Table 14.3.1.18 Summary of Treatment-Emergent Adverse Events Potentially Pertaining to Central Nervous System Depression by MedDRA System Organ Class and Preferred Term during the Treatment Period - Safety Analysis Set

Table 14.3.1.19 Summary of Treatment-Emergent Adverse Events Potentially Pertaining to Orthostatic Hypotension by MedDRA System Organ Class and Preferred Term during the Treatment Period - Safety Analysis Set

Table 14.3.1.20 Summary of Treatment-Emergent Adverse Events Regarding Psychiatry History Topic by MedDRA System Organ Class and Preferred Term during the Treatment Period - Safety Analysis Set

Table 14.3.2.1 Early Removal of Study Drug Depot – Safety Analysis Set

Table 14.3.3.1 Summary of Local Injection Site Tolerability Reactions During the Treatment Period- Safety Analysis Set

Figure 14.3.3.1 Percentage of Subjects Who Reported Local Injection Site Tolerability Reactions: Pain - Safety Analysis Set

Table 14.3.3.2 Summary of Local Injection Site Visual Analog Scale (VAS) Pain Scores - Safety Analysis Set

Figure 14.3.3.2 Mean Value of Local Injection Site Visual Analog Scale (VAS) Pain Scores by visit - Safety Analysis Set

Table 14.3.3.3 Summary of Local Injection Site Burning/Stinging Evaluation - Safety Analysis Set

Table 14.3.3.4 Summary of Injection Site Evaluation During the Treatment Period: Attempted Removal - Safety Analysis Set

Table 14.3.4.1 Incidence of Columbia Suicide Severity Rating Scale (C-SSRS): Suicidal Ideation and Suicidal Behavior - Safety Analysis Set

Table 14.3.4.2 Shift Table to Demonstrate Change in C-SSRS Categories from Baseline Lifetime During the Treatment Period - Safety Analysis Set

Table 14.3.4.3 Shift Table to Demonstrate Change in C-SSRS Categories from Baseline 6 months During the Treatment Period - Safety Analysis Set

Table 14.3.4.4 Shift Table to Demonstrate Change in C-SSRS Scores from Baseline lifetime During the Treatment Period - Safety Analysis Set

Table 14.3.4.5 Shift Table to Demonstrate Change in C-SSRS Scores from Baseline 6 months During the Treatment Period - Safety Analysis Set

